Statistical Analysis Plan

Clinical aspects, severity, management and outcome of febrile illnesses in the DRC

FIKI² ("Febrile illness in Kinshasa and Kimpese")

English translation for clinical trials.gov – unofficial translation – official document in French

Date: 2-March-2022

Authors: [name] (ITM Antwerp),
[name] (INRB, DRC),
[name] (INRB, DRC)

Approved by: Coordinating Investigator

Date: _____ / _____ / _____

Table of Contents

1. Introduction	3
2. Study design and objectives	3
3. Variables of interest	4
3.1. End points of the study	4
3.2. Primary variables	5
3.3. Secondary variables	5
3.4. Exploratory variables	5
4. Statistical analysis	6
4.1. Descriptive analyses	6
4.2. Primary analysis.....	6
4.3. Secondary analyses	6
4.4. Exploratory analyses	7

1. Introduction

This Statistical Analysis Plan (SAP) provides a detailed and comprehensive description of the main analyses pre-planned for the study entitled "Clinical aspects, severity, management and outcome of febrile illnesses in the DRC" (FIKI²). The current epidemiology and outcome of febrile illnesses in the Democratic Republic of Congo (DRC) is poorly documented. A better description of the causes, clinical presentation and host biomarker profiles will enable future studies targeting optimized diagnostic and therapeutic strategies.

These planned analyses will be carried out by statisticians from the Clinical Research Centre (CRC/INRB) and the Clinical Trials Unit of the Institute of Tropical Medicine (Antwerp). The results of the analysis will be described in a statistical analysis report, which will serve as a basis for major research publications. This document describes the statistical methods for the primary and secondary objectives of the study as defined in the protocol. Additional analyses may be carried out, but are not covered by the current analysis plan.

This analysis plan will be finalized and approved before the database for the first analyses is locked. Major changes in the statistical methodology used for the main and pre-planned analyses of this SAP will require detailed description and justification in the Statistical Analysis Report (SAR). The dataset, programs and final results will be archived in accordance with Good Clinical Practice guidelines (ICH E9).

2. Study design and objectives

2.1 Study design

Bi-centric (Kinshasa and Kimpese), prospective, observational cohort study of adults and children presenting to the emergency department or outpatient clinic with community-acquired febrile illness, with laboratory analyses and sample storage in a bio-bank.

A total of 1,500 people will be recruited for the study, including 1,000 children (< 18 years) and 500 adults. The study population consists of :

1. Children presenting with febrile illness in the pediatric emergency department of the Hôpital Général de Kinshasa (HGK / Mama Yemo) and in the outpatient and emergency departments of the Hôpital Général de Référence (HGR) of the Institut Médical Evangélique (IME), Kimpese, DRC.
2. Adults presenting with febrile illness at the outpatient and emergency departments of the General Reference Hospital (HGR) of the Evangelical Medical Institute (IME), Kimpese, DRC.

2.2 Objectives

Primary objectives

1. Estimate the proportion of survival with symptom resolution, assessed at day 21, of febrile illnesses.
2. Describe the biomarker profile (CRP, white blood cell count with differentiation) when including patients with febrile illnesses.

Secondary objectives

1. Estimate the proportion of symptom-free survival and death, assessed at day 21, for febrile illnesses.
2. Estimate the proportion of survival with symptom resolution, survival with symptom nonresolution, and death, assessed on days 7 and 14, of febrile illnesses.
3. Describe the epidemiology, clinical aspects, severity and management of febrile illnesses.
4. Identify factors associated with outcomes (resolution, non-resolution, death) of febrile illnesses.
5. Determine the frequency and profile of malaria (by rapid diagnostic test and thick drop), including co-infection, in patients with febrile illnesses.
6. Observe the association of CRP and WBC values with patient outcome at day 21.
7. Observe the association of CRP and WBC values with specific etiologies (malaria, bacteremia, dengue fever, etc.).

Exploratory objectives

1. Describe the frequency, etiology and antibiotic resistance patterns of community-acquired bacteremia detected in patients with febrile illnesses.
2. Assessing the performance and potential contribution of a rapid immunochromatographic test targeting dengue under field conditions in the DRC.
3. Evaluate metagenomic sequencing for the detection of pathogens causing febrile illness (with primary focus on RNA viruses).

3. Variables of interest

3.1. Final points of the study

Patients enrolled in the study will be monitored and evaluated at 4 points in time: at admission D0, at seventh follow-up day D7, at fourteenth follow-up day D14 and at twenty-first follow-up day D21. They will be categorized into 3 groups:

- **Resolution:** means (i) signs and symptoms have completely disappeared and treatment has been completed; or (ii) some signs or symptoms persist and/or treatment is still underway, but a marked improvement in these signs and symptoms suggests that the person will recover rapidly without the need for further investigation or treatment other than that already administered.
- **Non-resolution:** any combination other than those described for the "Resolution" option.
- **Deaths**

Patients with no clinical outcome (lost to follow-up, withdrawal of consent, etc.) will be excluded from analyses that include outcome. Additional sensitivity analyses will be carried out (section 4.5).

3.2. Primary variables

The primary variables in this study are of two types:

- Clinical: Clinical outcome on day 21 as described in section 3.1.
- Biological: CRP level, differentiated white blood cell count on admission

3.3. Secondary variables

- Socio-demographic characteristics: age, gender, geographical location
- Clinical outcome on days 7 and 14:
 - o Resolution: means (i) signs and symptoms have completely disappeared and treatment has been completed; or (ii) some signs or symptoms persist and/or treatment is still underway, but a marked improvement in these signs and symptoms suggests that the person will recover rapidly without the need for further investigation or treatment other than that already administered.
 - o Non-resolution: any combination other than those described for the "Resolution" option.
 - o Deaths
- Clinical: comorbidity, signs and symptoms on admission (these are the symptoms presented by a febrile patient enrolled in the study), as described in section 3.1.
- Diagnostic hypotheses at inclusion and final diagnoses
- Therapeutic journey prior to admission (visit to health center, treatment prior to presentation, etc.).
- Disease severity on days 0, 7, 14 and 21
 - Adults:*
 - o Simplified ambulatory severity index (SAHI)
 - o Quick Sepsis Related Organ Failure Assessment (qSOFA)
 - In children under 5 years of age:*
 - o Criteria of the algorithm for the management of childhood illnesses (ALMANACH)
- Initial and secondary hospitalization (assessed on day 21)
- Length of hospital stay (initial and/or secondary hospitalization) assessed on **day 21**
- Number of secondary visits (assessed on **day 21**)
- Number, types and results of laboratory and radiology tests prescribed/actually performed
- Number and types of medications and supportive care prescribed/actually administered
- Malaria detection by rapid test (HRP II antigen, pLDH antigen) and thick drop (type and parasitaemia)
- Hemoglobin level

3.4. Exploratory variables

- Number of patients from whom blood cultures were taken, proportion of positive blood cultures, identification of germs from positive blood cultures and resistance

profile

- Antibiotic resistance of identified germs (per bacteremia)
- NS1 and IgM antigen results for the detection of dengue by rapid test
- Pathogens causing febrile illness by metagenomic sequencing

4. Statistical analysis

4.1. Descriptive analysis

Baseline demographic and clinical characteristics will be described in terms of medians and interquartile ranges for continuous characteristics, and in terms of numbers and percentages for categorical characteristics. Selected baseline demographic and clinical characteristics will be compared between clinical outcome groups: survival with symptom resolution vs. survival without symptom resolution, and survival with symptom resolution vs. death. In addition, other clinical outcome groupings will be explored for comparisons, such as survival vs. death, or resolution vs. non-resolution. Comparisons between groups will be made using the Mann-Whitney test for continuous characteristics and the Chi-square test or Fisher's exact test for categorical characteristics for the three different strata (combination of site and age group) and for the whole cohort.

4.2. Primary analysis

The proportion of survival with symptom resolution, assessed at day 21, will be estimated as a proportion. The numerator will be the number of survivors who meet the definition of resolved, and the denominator will be the number who have completed the visit by day 21. The 95% confidence intervals for the proportion will be estimated using Wilson's method. A worst-case sensitivity analysis will also be carried out, defining all missing outcomes at day 21 as deaths, to examine the robustness of the results.

CRP and WBC values at recruitment will be described and compared using descriptive methods (see section 4.1). Different variables will be explored to compare CRP and WBC values, including clinical outcome, age, site, severity, diagnosis and others.

4.3. Secondary analysis

Estimate the proportion of symptom-free survival and death, assessed at day 21, for febrile illnesses.

The frequencies and proportions of survival (with 95% CI) of febrile patients with non-resolution of symptoms and of deaths assessed at day 21 will be presented. Confidence intervals for the proportions will be estimated using Wilson's method.

Estimate the proportion of survival with symptom resolution, survival with symptom nonresolution, and death, assessed on days 7 and 14, of febrile illnesses.

The frequencies and proportions (with 95% CI) of survival of febrile patients with symptom resolution, symptom non-resolution and death assessed at day 7 and day 14 will be presented. Confidence intervals for the proportions will be estimated using Wilson's method.

Describe the epidemiology, clinical aspects, severity and management of febrile illnesses.

Standard descriptive statistics will be used to describe this objective (see section 4.1).

Identify factors associated with outcomes (resolution, non-resolution, death) of febrile illnesses.

Univariate and multivariate logistic regressions will be used to analyze the association between baseline characteristics and the outcome of febrile patients (resolution, non-resolution and death) at day 21. Two different outcomes will be used in this process: resolution vs. non-resolution (excluding death) and death vs. survival. Potential predictors will be (non-exhaustive list):

- *Specific diagnosis (e.g. complicated malaria vs. others)*
- *Syndromic diagnosis (undifferentiated fever vs. others - neurological syndrome vs. others - respiratory syndrome vs. others)*
- *Almanach score for children under 5 years of age*
- *Modified ASAPS score and qSOFA in adults*
- *Outpatient consultation prior to admission*
- *Blood culture positive*
- *Presence of comorbidity*
- *Age*
- *Education level*
- *Hemoglobin level*

Determine the frequency and profile of malaria (by rapid diagnostic test and thick drop), including co-infection, in patients with febrile illnesses.

The frequency and proportion (with 95% CI) of malaria (simple and complicated; with or without hyperparasitemia) diagnosed by RDT and by thick drop and of malaria co-infections in febrile patients will be presented. Confidence intervals for the proportions will be estimated using Wilson's method.

Observe the association of CRP and WBC values with patient outcome at day 21.

The association between CRP values and white blood cell counts at day 21 to assess the link between these two values and individuals with outcomes of resolution, non-resolution and death will be examined with the Kruskal-Wallis test for continuous variables or Fisher's exact test for categorical variables. The outcome variables used for this comparison are *resolution vs. non-resolution (excluding death) and death vs. survival*.

Observe the association of CRP and WBC values with specific etiologies (malaria, bacteremia, dengue fever, etc.).

The association between CRP values and white blood cell counts with specific etiologies: malaria (simple + complicated), bacteremia, arbovirosis, other diagnoses will be examined with the Mann-Whitney test.

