## 6.3 Sample size and power

Taking into account the main and strategic aims of this study (to describe the presentations and issues on the 2 sites, initiate the research capacity of the teams, provide the bases epidemiological studies), the expected sample size is based on the budget, reality and logistical feasibility. Size refers to the number of participants recruited in the laboratory phase of the study (following amendment 1 of the protocol). We plan to include 500 children at HGK / Mama Yemo, and 500 at HGR-IME + health centers in Kimpese. children + 500 adults for a one-year study period. This number is sufficient to provide data relevant to the study's objectives, and will also enable teams to manage study requirements. With an expected drop-out rate of 20%, we hope to have an accuracy of at least less  $\pm$  4.9% in each stratum (combination of site and age group) in the estimation of the proportion of the primary result.

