4.6. Multiplicity and missing data

An analysis of all available cases will be the primary analysis for all objectives. Missing data in all data points, except clinical status, will be flagged and, in cases of limited missing data, multiple imputation will be used to recover the data. A subsequent analysis with the full set of imputed data will be performed and compared to the primary analysis. Results will be adjusted for multiplicity using the Holm-Bonferroni method.

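### Available-case death proportions in SAP 4.3 tend to overstate mortality when loss accrues over follow-up, and the SAP omits the protocol's Kaplan-Meier estimate that would correct this

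*SAP*

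**What the plan says.** SAP 4.3 plans simple proportions with 95% Wilson intervals for febrile patients with "non-resolution of symptoms and of deaths assessed at day 21 will be presented". For the earlier visits, resolution, "symptom non-resolution and death assessed at day 7 and day 14 will be presented" in the same form. The section gives no denominator.

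Two general rules apply. SAP 3.1: "Patients with no clinical outcome (lost to follow-up, withdrawal of consent, etc.) will be excluded from analyses that include outcome". SAP 4.6: "An analysis of all available cases will be the primary analysis for all objectives". The only stated denominator is in SAP 4.2, for the primary endpoint: "the denominator will be the number who have completed the visit by day 21". It does not say how a patient who died before that visit is counted.

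The worst-case analysis in SAP 4.2 defines missing day-21 outcomes as deaths. SAP 3.1 points to further sensitivity analyses in section 4.5, but that section covers subgroups.

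Protocol 6.2 plans Wilson proportions for the three outcome categories and also Kaplan-Meier estimates of survival and resolution over time. The SAP does not mention Kaplan-Meier. Protocol 6.3 gives the expected loss: "With an expected drop-out rate of 20%, we hope to have an accuracy of at least less" (the figure that follows is ±4.9% in each stratum).

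**The concern.** A death recorded on day 3 is a known outcome at days 7, 14 and 21. A patient alive on day 3 enters the day-21 proportion only if still in contact then. Protocol 5.1 widens the gap: inpatients are seen daily, so an in-hospital death is known at once, whereas outpatients and discharged patients must be reached at days 7, 14 and 21. When loss accumulates over the three weeks, the denominator gives up proportionally more survivors than deaths, even if loss has nothing to do with illness course.

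Mortality at the three visits belongs to the first two secondary objectives, and the protocol's strategic objectives want baseline outcomes for later studies. An inflated estimate would carry over into those studies. Because the excess grows with loss, strata with equal risk but unequal loss could also appear to differ.

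**Working it through.** **Inputs**
- 500 patients in each of three strata, 20% drop-out: Protocol 6.3.
- Wilson 95% interval, available cases: SAP 4.3, 3.1 and 4.6.
- True 21-day mortality *d*: assumed 4%, range 1% to 12%. The documents give no value for this cohort; the 12% in Protocol 1.1 concerns hospitalised undifferentiated fever.
- Timing of deaths: assumed uniform over 21 days, or early (exponential truncated at day 21, scale 3 or 5 days).
- Recorded deaths count as available cases: assumed.

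**The plan's own figure.** 500 × 0.80 = 400, and 1.96 × √(0.25/400) = 0.049. The ±4.9% reproduces.

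**Estimator.** Let *c* be the share of deaths by day 21 that are recorded, with 80% of survivors still in contact. The available-case proportion is

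*dc* / (*dc* + (1 − *d*) × 0.80).

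It equals *d* when *c* = 0.80 and exceeds *d* when *c* > 0.80.

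**Values of *c***
- Continuous loss: hazard −ln(0.80)/21 = 0.0106 per day, and *c* is the mean probability of not yet being lost at death. For uniform deaths, *c* = 0.20/0.2231 = 0.896.
- Loss at contacts: each contact is reached with probability 0.80^(1/3) = 0.928, loss is permanent, and a death is learned at the next contact. For uniform deaths, *c* = (0.928 + 0.862 + 0.800)/3 = 0.863. For scale 5, the weekly shares of deaths are 0.765, 0.189 and 0.047, so *c* = 0.765 × 0.928 + 0.189 × 0.862 + 0.047 × 0.800 = 0.910.

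**Day 21, *d* = 4%** (survivors seen: 0.96 × 0.80 = 0.768)

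| Loss pattern | *c* | Calculation | Estimate | Ratio |
|---|---|---|---|---|
| Ceiling: every death recorded, loss only among survivors | 1.00 | 0.0400/0.8080 | 4.95% | 1.24 |
| Continuous, early deaths (scale 3) | 0.969 | 0.0388/0.8068 | 4.81% | 1.20 |
| Continuous, early deaths (scale 5) | 0.952 | 0.0381/0.8061 | 4.73% | 1.18 |
| Continuous, uniform deaths | 0.896 | 0.0359/0.8039 | 4.46% | 1.11 |
| Contacts, early deaths (scale 5) | 0.910 | 0.0364/0.8044 | 4.52% | 1.13 |
| Contacts, uniform deaths | 0.863 | 0.0345/0.8025 | 4.30% | 1.08 |
| Loss fixed at enrolment | 0.80 | 0.0320/0.8000 | 4.00% | 1.00 |
| 30% of deaths unascertained | 0.70 | 0.0280/0.7960 | 3.5% | 0.88 |
| 40% of deaths unascertained | 0.60 | 0.0240/0.7920 | 3.0% | 0.76 |

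For *c* from 0.863 to 0.969, a true 1% reads 1.1% to 1.2%, and a true 12% reads 12.8% to 14.2%.

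**Earlier visits.** The ratio at day 14 is 1.08 to 1.12 under continuous loss and 1.04 to 1.07 under contact-based loss. At day 7 it is 1.04 to 1.05 and exactly 1.00.

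**Interval coverage** (20,000 simulated cohorts per case, *d* = 4%; uniform, scale 3 and scale 5 deaths). Continuous loss: 84% to 91% in a stratum of 500 and 69% to 86% in 1,500. Contact-based loss: 89% to 93% and 81% to 91%. Ceiling: 81% and 60%.

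**Bounds.** Counting missing as dead gives 1 − 0.768 = 23.2% whatever *c* is. Counting missing as alive gives *dc*, which is 3.5% to 3.9% in the five loss-over-time rows.

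**Check of the remedy.** With one million simulated patients, 5% true mortality, early deaths (scale 5) and continuous loss, Kaplan-Meier gave 5.02% and the available-case proportion 5.92%. For the survivor categories, take true values of 90% resolved, 6% unresolved and 4% dead with 20% of survivors lost: 0.96 × 0.72/(0.72 + 0.048) = 0.90, the true value.

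**The case against.** A reader might infer that deaths never leave the denominator, so that mortality is too high at all three visits under any random loss. The documents do not support that. Under Protocol 4.5 a participant no longer available for visits is lost to follow-up, with no exception for one who dies later. Such a death has no recorded outcome and is excluded under SAP 3.1. If missingness is independent of vital status there is no bias, and for outpatients whose death is learned only at the first contact there is none at day 7. If relatives of the dead are harder to reach than survivors, the sign reverses. The documents do not say which pattern will hold.

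Three further points have force. SAP 4.3 states no denominator, and the SAP 4.2 wording, read literally, could leave out earlier deaths. The excess of 0.3 to 0.8 percentage points lies well inside one stratum's sampling error: 16 deaths in 400 has a Wilson interval of 2.5% to 6.4%. And SAP 4.3 reports frequencies, so a reader could divide deaths by enrolment to obtain a lower bound.

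These points limit the certainty and the size, but they do not remove the problem. The excess persists in models that let deaths after loss go missing. The missing-as-death analysis cannot reveal it. The protocol's method that handles loss over time is absent from the SAP.

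**Conclusion.** The point holds in conditional form. If recorded deaths are counted and loss accrues over follow-up independently of death, the proportions in SAP 4.3 overstate mortality. With the plan's 20% drop-out and an assumed true 4%, the day-21 estimate is about 4.3% to 4.8%, a relative excess of roughly 8% to 20%. The 4.95% figure and the 81% and 60% coverage belong to the ceiling case and should not be read as expected values.

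A flat statement that the plan overstates mortality, or that a site with more loss will appear to have higher mortality, goes beyond the documents. Mortality level, timing of deaths and loss pattern are all assumptions here. What can be read directly is that the death denominator is undefined and that the SAP leaves out the Kaplan-Meier analysis of Protocol 6.2. This concerns secondary endpoints and is cheap to repair.

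**What to change.** In SAP 4.3:
- State that a known death is carried forward and belongs in the denominator at every later visit. Align the wording of SAP 4.2 with this.
- Make 1 minus the Kaplan-Meier survival estimate the main estimate of death by days 7, 14 and 21, by stratum, censoring at the last contact with known vital status, with a log-log 95% interval.
- Estimate the two survivor categories as (1 − Kaplan-Meier death) × the share resolved or unresolved among survivors with known status, with bootstrap intervals, so that the three categories sum to 100%. Say how the day-21 resolution figure relates to the primary estimate in SAP 4.2.
- Keep the crude available-case proportions with Wilson intervals as description.
- Add a bound that counts missing as alive beside the missing-as-death analysis. Kaplan-Meier assumes loss independent of death and does not correct loss that depends on vital status.
- Correct the SAP 3.1 cross-reference to section 4.5.

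The cost is SAP wording and a few lines of code. The Wilson interval, which Protocol 6.2 names for these proportions, would no longer be the main one, and the SAP should say so. Protocol 5.1 lists status at each contact but not date of death, so the team must confirm that the dates of death and of last contact are recorded.

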	
subsequent studies focused on optimizing diagnostics (biomarkers, platforms, etc.) or therapeutic interventions.
 
Primary endpoints
 
 
• Proportion of survival with symptom resolution evaluated on day 21, febrile illnesses.
 
• CRP and white blood cell values with differentiation on day 0 (inclusion).
 
 
Secondary endpoints
 
 
• Clinical status on a 3-category ordinal scale (resolution, non-resolution, death) evaluated on days 7, 14 and 21.
 
• Diagnostic hypotheses at inclusion and diagnoses final.
 
• Disease severity on days 0, 7, 14 and 21. 
 
- in adults : 
 
○ Simplified ambulatory severity index (SAHI)
 
○ Quick Sepsis Related Organ Failure Assessment (qSOFA)
 
 
 
- in children under 5 years of age: 
 
○ criteria of the algorithm for managing childhood illnesses (ALMANACH)
 
 
 
 
 
• Initial and secondary hospitalization (assessed on day 21).
 
• Length of hospital stay (initial hospitalization and/or secondary) (assessed on day 21).
 
• Number of secondary visits (assessed on day 21).
 
• Number and types of laboratory and radiology tests prescribed / actually carried out.
 
• Number and types of medications and supportive care prescribed / actually administered.
 
• Detection of malaria by rapid test (HRP II antigen), pLDH antigen) and by thick drop (type and parasitaemia).
 
 
Exploratory judgment criteria
 
 
• Frequency of bacteremia, with etiological distribution and antibiotic resistance profiles of germs identified.
 
• Detection of dengue by rapid test (NS1 antigen), IgG and IgM antibodies).
 
• Detection and profiling of disease-causing pathogens by metagenomic sequencing.
 

INCLUSION CRITERIA AND EXCLUSION	
Inclusion criteria:
 
 
• Ongoing fever detected on presentation, or documented at home or in another health center within 24 hours of presentation, defined by: temperature
 

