### 4.3 Inclusion and exclusion criteria

#### Inclusion criteria

- Fever in progress and objectified at presentation, or documented at home or in another location  
health care facility/24 hours of presentation defined by:  
*OR*
  - Oral or rectal temperature  $> 38^{\circ}\text{C}$*AND*
- Possibility of contact between the patient (or his or her designated relative) and the team responsible for
- study on days 7, 14 and 21.  
Informed consent signed by patient (adults) or legal representative acceptable (children or patients whose condition does not allow them to sign informed consent),

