#### Exclusion criteria

with the consent of children aged 12 and over, wherever possible

- Children under two months old.
- Hospitalization  $> 48$  h in the last 14 days (to exclude nosocomial fevers).

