## **5. STUDY PROCEDURES**

### **5.1 Study/visit schedule**

#### **Inclusion visit**

Participants will be included in the study as soon as the consent form has been signed. The study investigator or his or her representative will fill in the data collection form (box report form (CRF), the patient's demographic information, history, symptoms and signs (type and severity), co-morbidities, initial diagnosis, medications and examinations and his immediate decision (hospitalization or discharge).

The study team will work with patients to arrange the following contacts on days 7, 14 and 21.

- For patients with whom telephone contact is considered possible, the study team records the patient's telephone number and the number of the telephone number of one or more relatives authorized by the patient to provide information on health status up to day 21. Patients will also receive the member of staff responsible for the study.
- Patients for whom telephone contact is not an option will receive offer to return to the study center on days 7, 14 and 21. Home visits by community health workers participating in the study will also be considered if necessary and feasible.
- If the participant gives permission for the laboratory part of the study, a blood sample will be taken. (venous +/- capillary blood) is taken during the inclusion visit. This blood test is integrated with the routine sampling required for patient management. Immediate test results (CRP, white blood cell count with differentiation), blood cultures, thick drop, malaria RDT, dengue RDT) will be collected in the and some of them (hemocultures) communicated directly to the clinicians at study. Samples stored for further analysis (metagenomic evaluation) or of secondary research will be registered in the ITM biobank and the institutions research partners, depending on the logistical capacities being developed and well-established memorandums of understanding (based on existing collaborations).

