### 6.1 Variables of interest

- Demographic characteristics
- Basic clinical data (previous treatment, history, symptoms, clinical examination)
- Diagnostic hypothesis
- Patient outcome
- Examinations and treatments prescribed and carried out
- Outcome (survival with symptom resolution, survival without symptom resolution, death)

- Results of inflammatory biomarker analyses: CRP, white blood cells, and differentiation
- Results of etiological analyses: malaria, blood cultures, and germ antibiograms identified, metagenomic analysis, dengue TDR

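### The CRP and white-cell comparisons with outcome and etiology make no use of antimicrobial treatment before inclusion, although the study collects it and it can confound them

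*SAP*

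**What the plan says.** **Entry.** The Protocol synopsis requires "Ongoing fever detected on presentation, or documented at home or in another health center within 24 hours of presentation". Section 4.3 says much the same and sets no upper limit on days of illness. The only exclusion that touches earlier care is a hospital stay above 48 hours in the previous 14 days, which is there "to exclude nosocomial fevers". Outpatient treatment before presentation is allowed.

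**Sampling.** Study blood is drawn once, at inclusion. Protocol 5.1 states that follow-up visits have no laboratory procedures.

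**What is collected.** Protocol 6.1 lists "Basic clinical data (previous treatment, history, symptoms, clinical examination". SAP 3.3 lists "Therapeutic journey prior to admission (visit to health center, treatment prior to presentation, etc".

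**What is tested.** For objective 7 (etiologies), CRP and white cells in malaria, "bacteremia, arbovirosis, other diagnoses will be examined with the Mann-Whitney test". For objective 6 (day-21 outcome), they "will be examined with the Kruskal-Wallis test for continuous variables", with resolution vs. non-resolution and death vs. survival as the two contrasts. No covariate is named for either objective. SAP 4.5 presents every analysis by site and age group.

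**What was announced.** Protocol section 6 says that the SAP will describe statistical adjustment and the handling of confounders. For these tests the SAP does not.

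**The concern.** A patient who took an antibiotic or antimalarial before inclusion may be less likely to have a positive culture or slide. The same treatment may change CRP and white cells on day 0. Prior treatment can therefore act on both sides of the comparison.

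Two separate problems follow:

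- **Confounding.** Patients labelled positive contain a different share of pre-treated patients from those labelled negative. A marker difference can then appear with no link to etiology.
- **Lost labels.** A pre-treated patient who has bacteraemia but a negative culture is counted in the comparison group.

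For outcome (objective 6) there is no lost label. Confounding can still arise if prior treatment is related both to the day-0 marker and to recovery or death.

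At stake is the interpretation of two secondary objectives. Protocol 1.2 also looks ahead to using these markers to predict culture positivity.

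**Working it through.** **The plan's own figure.** The main study's only design figure is a precision of ±4.9% per stratum for the primary proportion. With 500 × (1 − 0.20) = 400 patients and p = 0.5, 1.96 × √(0.25/400) = 4.9%, so it reproduces. The plan gives no figure for the CRP and white-cell tests, so the rest is illustration.

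**Assumed inputs (none is in the documents).** Label frequency in untreated patients 10%. Share pre-treated (pT) 20, 40 or 60%. Treatment lowers the log marker by 0.3 or 0.5 SD and label detection by a fraction r of 30, 50 or 60%. Group sizes are 500 (one stratum) and 1,500 (whole cohort, simulated without site or age differences).

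**Step 1: where the confounding comes from.** Take pT = 0.6, r = 0.6, shift 0.5 SD, and no relation between marker and label within treatment groups.

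- Label-positive: 0.4 × 0.10 + 0.6 × 0.10 × 0.4 = 0.040 + 0.024 = 0.064.
- Pre-treated share: 0.024/0.064 = 37.5% of positives and (0.600 − 0.024)/0.936 = 61.5% of negatives.
- Spurious mean gap: 0.5 × (0.615 − 0.375) = 0.12 SD.

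**Step 2: false-positive rate of the two-sided 5% test.** 3,000 simulated studies per setting; Monte Carlo standard error at 9.1% is √(0.091 × 0.909/3000) = 0.5 points. Stratified means van Elteren on prior treatment.

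| pT / shift / r | n=500 crude | n=500 stratified | n=1,500 crude | n=1,500 stratified |
|---|---|---|---|---|
| 20% / 0.3 / 30% | 5.0% | 4.7% | 5.2% | 4.8% |
| 20% / 0.5 / 50% | 5.8% | 5.2% | 7.7% | 5.0% |
| 20% / 0.5 / 60% | 6.1% | 5.4% | 9.3% | 4.6% |
| 40% / 0.3 / 30% | 5.2% | 5.0% | 5.9% | 4.7% |
| 40% / 0.5 / 50% | 7.7% | 4.9% | 12.6% | 5.5% |
| 40% / 0.5 / 60% | 8.5% | 5.0% | 16.9% | 5.0% |
| 60% / 0.3 / 30% | 5.0% | 5.4% | 6.0% | 4.9% |
| 60% / 0.5 / 50% | 7.4% | 4.6% | 13.6% | 4.7% |
| 60% / 0.5 / 60% | 9.1% | 5.0% | 19.8% | 4.6% |

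These ranges are not bounds. With half the patients pre-treated, label frequency 8% untreated and 4% pre-treated, and CRP lowered two- to threefold (log SD 1.2), the crude rate is about 8 to 12% at 500 and 15 to 28% at 1,500.

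**Step 3: lost labels.** Let true bacteraemia be 10% and raise the log marker by 1 SD. The true concordance is Φ(1/√2) = 0.760. Let treatment lower the marker by d = 0 or 0.5 SD in bacteraemic patients only. With pT = 0.6, r = 0.3 and d = 0.5, the positives are 0.040 at mean 1 and 0.042 at mean 0.5; the negatives are 0.900 at mean 0 and 0.018 at mean 0.5. With Φ(0.5/√2) = 0.638:

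[0.040 × (0.900 × 0.760 + 0.018 × 0.638) + 0.042 × (0.900 × 0.638 + 0.018 × 0.5)] / (0.082 × 0.918) = 0.695.

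Over pT of 20 to 60%, r of 30 or 60% and both values of d, crude concordance is 0.695 to 0.759. In untreated patients it stays at 0.760; in pre-treated patients it is 0.630 to 0.752. Stratifying does not bring the lost cases back, whereas restricting to untreated patients avoids this loss.

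White cells, malaria, dengue and the outcome contrasts were not calculated separately.

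**The case against.** The strongest reply is that objectives 6 and 7 only set out to observe associations, and that the SAP already leaves room. Section 4.2 explores CRP and white cells by an open list of variables, the objective 4 predictor list is non-exhaustive, and the introduction permits further analyses. That is true, but permission is not pre-specification. Prior treatment is named in no CRP or white-cell analysis. The nearest listed item, an earlier outpatient consultation, belongs to the outcome regression and is not the same as having taken an antimicrobial.

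Other parts of the reply stand:

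- **Prediction.** For predicting observed culture positivity in patients as they present, the crude association is a legitimate quantity. A reader might infer that the aim in Protocol 1.2 is answered with a biased estimate. That holds only if the target is true bacteraemia or the effect of etiology on the marker.
- **Frequencies.** A reader might infer that bacteraemia and malaria are reported only as overall proportions. SAP 4.5 splits them by site and age group, though not by prior treatment.
- **Size and direction.** With mild inputs the crude test stays near its nominal level. Holm-Bonferroni (SAP 4.6) would lower all the rates shown, without removing confounding. Patients still febrile after treatment could be treatment failures with higher CRP, which would reverse the bias. Cultures follow surveillance criteria (Protocol 5.3), so the number tested may be below 500 and the excess smaller.

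**Conclusion.** The point holds as a gap in pre-specification. The SAP leaves a collected baseline variable out of two comparisons that it can confound, although the protocol promised that confounders would be addressed. On the assumed inputs the crude false-positive rate is about 5 to 9% per stratum and 5 to 20% in the whole cohort. Stratified, it is 4.6 to 5.5%. A true concordance of 0.76 could read as 0.70 to 0.76. All these figures depend on inputs that the documents do not give.

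Three stronger readings are not supported:

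- **That illness day is recorded and ignored.** The readable text names no onset date or duration. The inclusion visit lists "demographic information, history, symptoms and signs (type and severity), co-morbidities", and the schedule figure is not shown.
- **That patients often arrive already treated.** Eligibility allows it, but no frequency is given.
- **That the results are distorted.** They can be; whether they are, and in which direction, is unknown.

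**What to change.** In SAP 4.3, define prior treatment as any antibiotic or antimalarial before inclusion (yes/no). Keep the crude comparisons and add:

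1. CRP and white-cell comparisons for objectives 6 and 7 stratified by prior treatment, with a van Elteren test.
2. A sensitivity analysis in patients without prior treatment, because stratification does not restore pre-treated cases with negative cultures or slides.
3. Bacteraemia and malaria frequencies by prior treatment.
4. Prior antimicrobial treatment as a named candidate predictor in the objective 4 models.

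Check whether the CRF holds an onset date. If it does, use days since onset as a single descriptive covariate and do not cross it with treatment and stratum. Two treatment groups × three onset bands × three strata would make 18 cells. At the 6.4% label frequency of step 1, a stratum has 0.064 × 500 = 32 positives, about five per cell (32/6).

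The cost is SAP wording, with no new sample or visit. The downsides are smaller groups and a variable that is partly self-reported, so some confounding will remain.
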